4.4 Dose Limiting Toxicity (DE phase only)

A DLT is a clinically significant adverse event (AE) or laboratory abnormality assessed by the Co-Principal Investigators as at least possibly related to the study drug and unrelated to disease progression, concurrent illness, or concomitant medications, occurring within Cycle 1. Toxicity will be graded and recorded according to the Toxicity Grading Scale for Healthy Adult and Adolescent Volunteers Enrolled in Preventative Vaccine Clinical Trials (presented in the companion Operations Manual), modified to include a systemic line item for rigors/chills and an amendment to the classification of pyrexia (Appendix 3). A DLT is defined as:

- Grade 3 or 4 adverse event, except for fatigue and fever and/or rigors/chills
- Grade 4, or an increase above baseline of 2 or more grades, fatigue
- Grade 4 fever and/or rigors/chills.

4.5 Dose Confirmation Phase (up to total of 3 cycles)

The DC phase will not begin until the Sponsor has submitted to the Ethics Committee and regulatory authority the requisite sub-chronic nonclinical safety data, and received approval to proceed to 3 cycles of dosing.

In the DC phase, up to 15 subjects will be recruited at the RP2D. The Safety Team will have the responsibility of reviewing safety data from the DC phase of the trial and making recommendations regarding dose modifications. If a DC phase subject withdraws from dosing within the first 2 cycles for reasons unrelated to drug toxicity, the subject may be replaced at the discretion of the Safety Review Team.

4.6 Intra-Subject Dose Reduction (DC phase only)

An individual subject's dose may be reduced to the next lower cohort dose level (ie, as determined from the DE phase), at the Co-Principal Investigator's discretion and with

the approval of the Sponsor, following a grade 4 or other clinically significant toxicity. The dose may not be reduced below 125 μ g/week.

4.7 Antipyretic Pre-Medication (DC phase only)

Subjects who experience an adverse event of pyrexia or rigors/chills (grade 3 or less) may receive the same dose level in subsequent dosing visits with antipyretic premedication, at the discretion of the Co-Principal investigators.

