DC phase subjects will be admitted to the unit the morning of dosing for a brief physical examination (Day 1 only), weight (Day 1 and Day 22), ECG and vital signs. Any adverse events and concomitant medications taken since the last visit will be recorded and eligibility confirmed. An MSFC, FSS, and EDSS will be performed on Day 1 of each cycle, and the SF-36 will be performed at the end of Cycle 3 only. An ophthalmologic examination, to consist of visual acuity determination, biomicroscopy, and dilated fundoscopy, will be performed within a week of the end of Cycle 3. (EDSS will be repeated following neurological examination at any visit where indicated by a change in functional status).

A cranial MRI will be performed at the end of Cycle 3 (details to be provided in the companion Radiology Manual of Operations).

An indwelling intravenous cannula will be sited in a forearm. A pre-dose blood sample will be taken for safety samples (Days 8 and 22 in Cycles 2 and 3, and End of Dosing or Early Discontinuation where applicable). A pre-dose blood sample for PD and immune parameter analysis will be taken on Day 22 of each cycle.

Version 5

Study drug will be drawn up and administered at the scheduled time by a slow intravenous infusion over 10 minutes. Subjects will be closely monitored for changes in their health or physiological status. At any time during dosing, the infusion rate can be reduced or turned off in response to an adverse event occurring. Once the infusion is completed, the cannula will be flushed with 0.9% sodium chloride for injection. The cannula will stay *in situ* until discharge.

Subjects will be required to remain in bed for four hours post dose and then will be allowed to mobilise gently around the unit.

Vital signs will be repeated mid-way through the infusion (5 mins), 15 and 30 minutes, 2 and 4 hours post-dose. ECG will be repeated at 4 hours post-dose. Adverse event enquiry will be completed mid-way through the infusion, 15 and 30 minutes post dose and ongoing throughout the inpatient stay.

Meals, snacks and drinks will be provided throughout the day.

Subjects will be discharged mid afternoon but may remain in the unit for up to 24 hours at the discretion of the Investigator.

6.5 Treatment Period -End of Dosing (Day 29) or Early Discharge-(7 +1 days following last dose of drug)

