14.4 Statistical Methods

14.4.1 General Overview and Plan of Analysis

Summary statistics will be presented to describe the analysis populations, namely, the ITT, SE, and CS populations. Tabulations will include the number of subjects, mean, standard deviation, minimum, median, and maximum for continuous variables; and/or frequency and percentage of subjects for categorical variables. Summary statistics for certain safety parameters will also be presented for the MTD population.

For all subjects, the data will be tabulated by dose cohort and for the total patient population.

All statistical analyses will be performed using SAS version 9.1 (or higher), unless specified otherwise. The use of other statistical software will not be considered a violation of the statistical analysis plan, nor require an amendment of this plan.

Version 5

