14.5.3.2 Adverse Events (AE)

"Adverse event" and "adverse experience" may be used interchangeably. All summary tables will be based on coded preferred terms, instead of verbatim terms. All adverse events will be coded, using MedDRA dictionary version 11.0. The use of another version will not be considered a violation of the statistical analysis plan, nor require an amendment to the plan. The categories and definitions of severity and causal relationship for all AEs, including the criteria for which an AE is to be classified as "serious", are as described in the protocol.

The overall incidence of adverse events will be tabulated by dose cohort and total population, including the number and percentage of subjects with at least one: adverse event, serious adverse event, or treatment-related adverse event. The number of deaths and discontinuations due to adverse event(s) will be presented. The incidence of adverse events by intensity/grade (Grades 1, 2, 3, and 4) and by relationship to study drug (not related, possibly related, and probably related), and the incidence of serious adverse events (SAEs) by relationship to study drug, will also be presented. DLTs will be identified in the AE/SAE listings. If there are multiple occurrences of the same AE for the same subject, only the first occurrence will be counted.

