14.5.3.4 Vital Signs

Vital signs, including changes from baseline to each subsequent timepoint, will be summarized for each dose level using descriptive statistics.

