Appendix 2 New York Heart Association Functional Classification (1994)

| NYHA Class | Symptoms |
|---------------|---|
| I | No symptoms and no limitation in ordinary physical activity, e.g. shortness of breath when walking, climbing stairs etc. |
| II | Mild symptoms (mild shortness of breath and/or angina) and slight limitation during ordinary activity. |
| 111 | Marked limitation in activity due to symptoms, even during less-than-ordinary activity, e.g. walking short distances (20-100 m). Comfortable only at rest. |
| IV | Severe limitations. Experiences symptoms even while at rest. Mostly bedbound patients. |

Version 5

Appendix 3 Toxicity Grading Scale for Healthy Adult and Adolescent Volunteers Enrolled in Preventative Vaccine Clinical Trials

(Source: Guidance for Industry issued by U.S. DHHS September 2007)

The tables within the guidance document do not include a systemic line item for rigors/chills. Rigors/chills should be graded in accordance with the following scale:

| Systemic (General) | Mild (Grade 1) | Moderate (Grade 2) | Severe (Grade 3) | Potentially Life Threatening (Grade 4) |
|-----------------------|-------------------|---|--|--|
| Rigors/Chills | Mild | Mild to Moderate, no antipyretic medication (paracetamol/NSAID) indicated | Moderate, antipyretic or corticosteroid indicated | Severe, symptomatic >4 hours despite treatment with antipyretic /corticosteroid |

The systemic line item for pyrexia has been amended in line with existing guidelines for adverse events associated with oncology studies (ECOG (http://ecog.dfci.harvard.edu/general/ctc.pdf) and NHI CTEP

(http://ctep.cancer.gov/protocolDevelopment/electronic_applications/ctc.htm)).

| Systemic (General) | Mild (Grade 1) | Moderate (Grade 2) | Severe (Grade 3) | Potentially Life Threatening (Grade 4) |
|-----------------------|-------------------|-----------------------|---------------------------|---|
| Fever (°C) | 37.1 – 38.0 | 38.1 – 40 | >40 for less than 24 h | >40 for more than 24h despite prophylaxis or treatment with antipyretics (paracetamol or NSAID) |

[The Guidance for Industry document "Toxicity Grading Scale for Healthy Adult and Adolescent Volunteers Enrolled in Preventative Vaccine Clinical Trials" is presented in the companion Operations Manual]

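### The dose-confirmation tables omit repeat fevers and chills, and they pool temperatures from infusions given with and without antipyretic cover

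*Protocol*

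**What the plan says.** Section 4.7 applies to the DC phase only. After pyrexia or rigors/chills of grade 3 or less, a subject "may receive the same dose level in subsequent dosing visits with antipyretic premedication, at the discretion of the Co-Principal investigators". No agent, dose, timing or stopping rule is given.

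The protocol then fixes how the results are summarised:

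- **AEs (Section 14.5.3.2).** Tables use coded preferred terms and are given overall, by grade and by relationship. The counting rule is: "If there are multiple occurrences of the same AE for the same subject, only the first occurrence will be counted". There is no worst-grade exception.
- **Temperature (Sections 7.5 and 14.5.3.4).** Temperature is one of the vital signs. "Vital signs, including changes from baseline to each subsequent timepoint, will be summarized for each dose level using descriptive statistics".
- **Strata (Section 14.4.1).** "For all subjects, the data will be tabulated by dose cohort and for the total patient population".

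No part of Section 14 mentions pre-medication. The raw data are collected, however. Section 6.4 states for the DC dosing visits of Cycles 2 and 3: "Any adverse events and concomitant medications taken since the last visit will be recorded". It also gives the reading times: "Vital signs will be repeated mid-way through the infusion (5 mins), 15 and 30 minutes, 2 and 4 hours post-dose". Section 6.3 has the same five times for Days 8, 15 and 22 of Cycle 1.

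**The concern.** Fever and chills are the expected reaction to this drug; Section 2.1 uses them to mark the desirable dose range. Section 2.3 gives the DC phase the task of showing that three months of dosing is safe and tolerable before a larger and longer trial. Section 7 promises to describe how often AEs occur, how severe they are and when.

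Cover under Section 4.7 starts only after a first event, and the AE tables stop counting that event at the same moment. They therefore cannot show whether the reaction came back at later infusions, at what grade, or under what cover. The temperature table does not fill the gap, because a fall in mean temperature over visits could reflect antipyretic cover or adaptation to the drug. The sponsor would need this information to decide whether the next trial's dosing instructions should include pre-medication.

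**Working it through.** **The plan's own figures.** The protocol states no number on this point. Its only computed table, the escalation probabilities in Section 14.1, is not involved. It reproduces from (1−p)³ + 3p(1−p)²·(1−p)³ at all nine rates: 90.6, 70.9, 49.4, 30.9, 17.2, 8.2, 3.2, 0.9 and 0.1%.

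**Step 1: how the rules interact.** Suppose a subject has a Grade 1 fever at dose 1, is pre-medicated from dose 2, and has a Grade 3 fever at dose 5. By Section 14.5.3.2 the dose-1 event is counted and the dose-5 event is not, so the by-grade table shows Grade 1. A recurrence of the triggering AE under Section 4.7 cover is always a later occurrence, so it is always dropped.

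**Step 2: ceilings.** Inputs: up to 15 DC subjects (Section 4.5) and up to 12 doses (Section 4.1).

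- DC infusions: 15 × 12 = 180.
- First doses, never covered under Section 4.7: 15.
- Most that could be covered: 15 × 11 = 165, and 165/180 = 91.7%.
- One subject covered from dose 2 onward: 11/180 = 6.1%.
- Infusions after a first event at dose k, where the AE table says nothing more about that reaction in that subject: 12 − k. For k = 1, 4 and 8 this is 11, 8 and 4 of 12 (92%, 67%, 33%).
- Temperature at doses 2–12: 11 × 5 readings = 55 by-visit rows, or up to 55 × 15 = 825 readings, that can mix covered and uncovered infusions.

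**Step 3: illustration with assumed inputs.** The protocol gives neither a reaction rate nor an effect of cover. Assume a constant, independent fever probability p at each uncovered infusion, cover always used after the first event, and relative risk r under cover.

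- Tabulated incidence = 1 − (1−p)¹². It does not contain r.
- Expected covered infusions per subject: C = 11 − Σ(1−p)ᵏ, k = 1 to 11.
- Expected events under cover per subject = r·p·C.

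| p | Tabulated incidence | C (share of 12) | Events under cover, r = 1 | r = 0.5 | r = 0.25 | r = 0 |
|---|---|---|---|---|---|---|
| 0.3 | 98.6% | 8.71 (73%) | 2.6 | 1.3 | 0.65 | 0 |
| 0.5 | about 100% | 10.0 (83%) | 5.0 | 2.5 | 1.25 | 0 |
| 0.8 | about 100% | 10.75 (90%) | 8.6 | 4.3 | 2.15 | 0 |

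A simulation of the same model agrees. Tabulated incidence is the same whether cover works fully or not at all. With p = 0.5 and r = 0.5, the fever rate falls from 50% at dose 1 to about 25% at dose 12 through cover alone, with no adaptation. A temperature summary by visit could not tell the two apart.

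**The case against.** The strongest reply is that this only asks for one more table. The protocol assigns a statistical analysis plan to a contractor (Section 14) and data-handling detail to a Data Management Plan (Section 18.4), and nothing forbids added output. First-occurrence counting is the usual way to avoid counting a subject twice. With at most 15 subjects the listings are readable, AE discontinuations are tabulated, and the Safety Review Team reviews DC safety.

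Much of this stands. The data are not lost, and the incidence tables should stay. It does not remove the point, because the protocol itself fixes the first-occurrence rule, applies it to grades without a worst-grade exception, and fixes the strata. Dropping a later, worse grade would be a fault without Section 4.7 too. It matters more here because treatment conditions can change after the first event.

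A reader might infer four stronger things that the documents do not support:

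- **That a split table would show whether cover was needed.** It would not. Covered subjects are chosen because they reacted, at investigator discretion, and what they would have experienced uncovered is unknown.
- **That most DC infusions will be covered.** The 165 of 180 requires every subject to react at dose 1 and be covered at all 11 later doses.
- **That AE grades in general are not comparable under cover.** Fever Grades 1–3 in Appendix 3 are temperature and duration bands that do not refer to antipyretics. At most the point touches rigors/chills (Grade 3 reads "Moderate, antipyretic or corticosteroid indicated") and Grade 4 fever, and the conclusion does not rest on it.
- **That the maximum tolerated dose is affected.** It comes from the dose-escalation phase, where Section 4.7 does not apply.

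**Conclusion.** The point holds as a fault in the stated summary rules. Recurrences of the triggering reaction, covered or not and of any grade, are absent from the planned AE tables. DC temperature summaries after dose 1 can mix covered and uncovered infusions, even if the DC phase has its own column. Following the rules as written could understate the severity and recurrence of the drug's main expected reaction, and could let antipyretic cover look like adaptation.

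The size cannot be stated beyond ceilings: 165 of 180 infusions, and 11 of 12 for a subject who first reacts at dose 1. The actual mix is unknown, and the illustration rests on assumed values of p and r. No sample size or error rate changes, and the first-event incidence of the triggering reaction is unaffected. This should be changed because it is cheap and serves the stated purpose of the DC phase; no subject's safety depends on it.

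**What to change.** 1. Keep the first-occurrence incidence tables, but use each subject's worst grade in the by-grade table.
2. Record antipyretic pre-medication for each infusion, with an indication that separates it from antipyretics given to treat an AE, which Section 5.4 also allows.
3. Add one descriptive DC table by dose number (1–12, denominator = subjects infused at that dose). Show all fever and rigors/chills occurrences by grade and the post-dose temperature change, flagged by pre-medication status.
4. Report the percentage of DC subjects and of DC infusions pre-medicated beside the tolerability conclusion.
5. Make no formal or causal comparison of covered with uncovered infusions.

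No new visit or assessment is needed, because temperature, AEs and concomitant medications are already recorded at each DC dosing visit. The cost is one indication entry on the case report form and one extra table. The downsides are small cells (at most 15 per dose, fewer by pre-medication status) and a tolerability statement that is conditional on pre-medication use.

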4.8 Safety Review Team

A Safety Review Team (SRT), comprising the Co-Principal Investigators, the Sponsor's Medical Monitor and an independent clinical expert will be empanelled. At the conclusion of each cohort in the DE phase, the SRT will meet by teleconference to determine from all available clinical safety and PD data:

- Whether the next cohort should be initiated
- If so, the increment of dose escalation
- If not, that the MTD has been achieved.

The SRT will further determine the progression to, dose, and size of the RP2D cohort; oversee subject safety during the DC phase; and recommend DC dose modifications as needed.

5. Study Population

5.1 Target population

The study aims to recruit between 27-33 male and female subjects over the age of 18 years, with a diagnosis of primary progressive or secondary progressive MS. All subjects who have received any quantity of study drug, whether withdrawn prematurely or not, will be included in the final safety analysis.

Subjects who receive study drug and are subsequently withdrawn are not permitted to be enrolled for a second time.

5.2 Inclusion Criteria

- 1. At least 18 years of age.
- 2. Diagnosis of MS, by the McDonald criteria¹⁷. (See Appendix 1)
- 3. Chronic progressive MS (CPMS), defined as either primary progressive MS (PPMS) or secondary progressive MS (SPMS), per the criteria of the National Multiple Sclerosis Society (USA) Advisory Committee on Clinical Trials of New

Version 5

Agents in Multiple Sclerosis¹⁸. [NOTE: In the dose-confirmation phase, only subjects with SPMS may be enrolled].

- 4. MS is clinically active with worsening clinical status within the past 2 years.
- 5. Expanded Disability Status Scale (EDSS) of 2.5 to 7.0 at Screening.
- 6. The following laboratory values must be documented within 3 days prior to initiation of study drug:
 - Absolute neutrophil count (ANC) \geq 1 x 10⁹/L
 - Platelet count $\geq 100 \times 10^9/L$
 - Serum creatinine \leq 1.5 mg/dL
 - AST (SGOT) and ALT (SGPT) $\leq 2 \times$ upper limit of normal.
- 7. Provide written informed consent to participate.
- 8. Willing to comply with scheduled visits, treatment plans, laboratory assessments, and other study-related procedures.

5.2 Exclusion Criteria

- 1. Relapsing-remitting MS or progressive-relapsing MS
- 2. Any immunomodulatory drug therapy or immunosuppressive therapy within the previous six months, or vaccine or systemic corticosteroids within the previous 60 days, prior to initiation of study drug.
- 3. Exposure to other experimental treatments currently under investigation in MS clinical trials, including alemtuzamab, rituximab, fingolimod, and cladribine.
- 4. A diagnosis or history of collagen vascular disease (including Sjögren's syndrome and systemic lupus erythematosus), anticardiolipin antibody syndrome, cerebral autosomal dominant arteriopathy with subcortical infarcts and leukoencephalopathy (CADASIL), sarcoidosis, vasculitis, Bechet's syndrome and/or Lyme disease.
- 5. History of alcohol or drug abuse (with the exception of cannabinoids) within 2 years prior to initiation of study drug.
- 6. Inability to refrain from smoking for the duration of the inpatient stay.
- 7. Major surgery or radiation therapy within 28 days prior to initiation of study drug.
- Active infection requiring antibiotics within 2 weeks prior to initiation of study drug.
- 9. Active malignancy within 2 years of entry, with the exception of basal cell carcinoma and squamous cell carcinoma of the skin
- 10. Uncontrolled congestive heart failure (New York Heart Association Classification 3 or 4 [Appendix 2]), angina, myocardial infarction, cerebrovascular accident, coronary/peripheral artery bypass graft surgery, or transient ischemic attack within 3 months prior to initiation of study drug.

- 11. Symptomatic cardiac dysrhythmias requiring treatment, or persistent prolongation of the QTcF (Frederica) interval to > 450 msec for males or > 470 msec for females.
- 12. In the Dose-Confirmation phase only, screening echocardiogram which shows abnormalities judged by the investigator to be clinically significant, including but not limited to a left ventricular ejection fraction below the testing facility's lower limit of normal.
- 13. Pregnant or lactating female.
- 14. Women of childbearing potential, unless surgically sterile for at least 3 months (i.e., tubal ligation), postmenopausal for at least 12 months (and follicle-stimulating hormone [FSH] > 20 U/mL), or unless they agree to use effective, dual contraceptive methods (i.e., oral, injectable, or barrier method with male partner using a condom) while on study drug.
- 15. Men of childbearing potential who partner with a woman of childbearing potential, unless they agree to use effective, dual contraceptive methods (i.e., a condom, with female partner using oral, injectable, or barrier method) while on study drug and for three months following discontinuation of study drug.
- 16. Known human immunodeficiency virus or acquired immunodeficiency syndrome-related illness.
- 17. Serological evidence of Hepatitis B, C or HIV infection.
- 18. Any severe, acute or chronic medical or psychiatric condition or laboratory abnormality that may increase the risk associated with study participation or study drug administration, may interfere with the informed consent process and/or with compliance with the requirements of the study, or may interfere with the interpretation of study results and, in the investigator's opinion, would make the patient inappropriate for entry into this study.
- 19. Previous exposure to MIS416.

